Endoscopy with biopsies (histology, IHC, RNA, EndoFLIP) ²		X ^{2, 2a, 4}									X ^{2, 2b}

Study Procedure	Screening Period		24-Week Double-Blind Treatment Period ¹⁸								
	Screening ¹ V1	Screening Endoscopy/ Biopsy ² V2	Baseline V3	V4	V5	V6	V7	V8	V9	V10	DB EOT V11 ³
Week (W)				W1	W2	W4	W8	W12	W16	W20	W24 ³
Day (D)	D-85 to D-29 ¹	D-21 ²	D1	D8	D15	D29	D57	D85	D113	D141	D169
Visit Window (Days [d])		±7 d		±3 d	±3 d	±3 d	±3 d	±3 d	±3 d	±3 d	+7 d
Safety: ^{7, 7a, 18}											
Vital signs ¹³	X	X	X ¹³	X ^{13, 13a}	X ^{13, 13a}	X ^{13, 13a}	X ^{13a}	X ^{13a}	X ^{13a}	X ^{13a}	X
Physical examination	X										X
ECG	X										X
Height	X										X ¹⁴
Weight	X	X	X		X	X	X	X	X	X	X
Adverse events	X	X	X	x	X	X	X	X	X	X	X
Laboratory Testing: ^{7, 7a}											
Hematology, Chemistry	X		X					X			X
Serology tests ¹⁵	X										
Serum FSH	X										
Pregnancy test ¹⁶	Serum	Urine	Urine			Urine	Urine	Urine	Urine	Urine	Urine
Urinalysis	X		X					X			X
PK and ADA: ^{7, 7a}											
PK sample			X					X			X
ADA sample			X					X			X
Biomarkers and Genomics: ^{7, 7a}											
Whole blood DNA (optional)			X								
Whole blood RNA (optional)	X		X								X
Plasma Eotaxin-3	X		X			X		X			X
Serum TARC	X		X			X					X
Serum Total IgE	X		X			X		X			X
Allergen-specific IgE, IgG4	X		X			X		X			X
Future Biomarker Serum/Plasma	X		X			X		X			X

ADA = anti-drug antibody; DB EOT = end of double-blind treatment period; DSQ = Dysphagia Symptom Questionnaire; ECG = electrocardiogram; EoE-EREFS = Eosinophilic Esophagitis-Endoscopic Reference Score; EQ-5D-3L = European Quality of Life 5-dimension (version 3L; 3-level); IHC = immunohistochemistry; PGIC = Patient Global Impression of Change of Dysphagia; PGIS = Patient Global Impression of Severity of Dysphagia; POEM =

Patient-Oriented Eczema Measure; PRO = patient-reported outcome; PK = pharmacokinetic; RQLQ(S)+12 = Rhinoconjunctivitis Quality of Life Questionnaire for patients aged 12+ years; TNSS = Total Nasal Symptom Score; V = visit

Table 2: Part C Schedule of Events – Extended Active Treatment Period

	28-Week Extended Active Treatment Period ¹⁴								
Study Procedure	V11 ¹	V12	V13	V14	V15	V16	V17	V18	EOT V19
Week (W)	W24 ¹	W26	W28	W32	W36	W40	W44	W48	W52
Day (D)	D169	D183	D197	D225	D253	D281	D309	D337	D365
Visit Window (Days [d])	+7 d	±7 d	±7 d	±7 d	±7 d	±7 d	±7 d	±7 d	+7 d
Treatment:²									
Administer study drug ^{3, 4, 4a}	X	X	X	X	X	X	X	X	
Study drug dispensation ^{4, 4a}	X	X	X	X	X	X	X	X	

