10.5. Additional Statistical Data Handling Conventions

The following analysis and data conventions will be followed:

Definition of baseline:

- The baseline assessment for each study part will be the latest, valid predose assessment available for the corresponding study part, respectively

General rules for handling missing data:

- If the start date of an AE or concomitant medication is incomplete or missing, it will be assumed to have occurred on or after the intake of study medication, except if an incomplete date (eg, month and year) clearly indicates that the event started prior to treatment. If the partial date indicates the same month or year of the intake of study medication date, then the start date by the study medication intake date will be imputed; otherwise, the missing day or month by the first day or the first month will be imputed.
- No imputations for missing laboratory data, ECG data, vital sign data, or physical examination data will be made.

Unscheduled assessments:

- Extra assessments (laboratory data or vital signs associated with non-protocol clinical visits or obtained in the course of investigating or managing AEs) will be included in listings and summaries. If more than 1 laboratory value is available for a given visit, the first observation will be used in summaries and all observations will be presented in listings.

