#### 4.5.2. Laboratory Safety Variables

Hematology, chemistry, urinalysis, and pregnancy testing samples will be analyzed by a central laboratory. Samples will be collected predose at the initial screening visit (visit 1), baseline visit (visit 3), week 12, week 24, week 36, week 52 (EOS) or ET visits. Tests will include:

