### 5.7.2. Clinical Laboratory Measurements

Laboratory measurements include clinical chemistry, hematology and urinalysis results, and will be converted to values in standard international units. Summaries of laboratory variables will include:

- Descriptive statistics of laboratory result and change from baseline by visit.
- The number (n) and percentage (%) of subjects with treatment-emergent PCSVs. This summary will be provided based on all patients in the SAF as well as in the subgroup of SAF patients who did not meet the PCSV criterion at baseline.
- Shift tables based on baseline normal/abnormal and other tabular and graphical methods may be used to present the results for parameters of interest

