### **6.4. Analysis Visit Windows**

Data analyzed by-visit-analysis (efficacy [excluding daily diary data], laboratory data, vital sign, ECG, ADA) will be summarized by the study scheduled visits described in study protocol and SAP Section 11.2, "Schedule of Event".

The analysis visit windows will be created per study schedule of events (SOE) table for each parameter and will be applied if the data from the study scheduled visits are unavailable. The following general rules will be applied to unscheduled visit and/or early termination (ET) visit mapping for each parameter:

1. If ET visit falls in an analysis window which has no missing value of this parameter, ET will be mapped to the next scheduled visit.
2. If both ET visit and unscheduled visit of the same parameter are available in the same analysis visit window, only ET visit will be mapped.

3. If multiple unscheduled visits of the same parameter are available in the same analysis visit window, the unscheduled visits will be mapped using the following rules:
  - a. The closest unscheduled visit from the target day will be selected.
  - b. If multiple unscheduled visits exist on the same day, the first unscheduled visit will be used.
4. If mapping distance is greater than 4 weeks, the unscheduled visit will not be mapped.

Unscheduled visits and early termination (ET) visit will be mapped per the analysis visit windows for Part B and Part C (Table 1-5) based on the study day/visit of each parameter, respectively.

Due to COVID-19 pandemic, patients may have delayed week 24 visit and week 52 visit. The two visits will not be remapped for primary analysis of efficacy.

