**Table 2: Analysis Visit Window for Safety and Biomarkers in Part B**

Visit from SOE	Target Study Day in Part B a	Analysis Window based on Study Day in Part B					
		Vital signs	Weight	Physical examination, ECG, Height	Laboratory, PK, ADA	Eotaxin-3, Total IgE, Allergen-specific IgE, IgG4	TARC
Baseline	1	≤1	≤1	≤1	≤1	≤1	≤1
Week 1	8	[2, 11]					
Week 2	15	[12, 22]	[2, 22]				
Week 4	29	[23, 43]	[23, 43]			[2, 57]	[2, 89]
Week 8	57	[44, 71]	[44, 71]				
Week 12	85	[72, 99]	[72, 99]		[2, 113]	[58, 127]	
Week 16	113	[100, 127]	[100, 127]				
Week 20	141	[128, 155]	[128, 155]		[114, 155]		
Week 24 (Part B end of treatment)	169	[156, 190] Error! Reference source not found.	[156, 190] Error! Reference source not found.	[2, 190] Error! Reference source not found.	[156, 190] Error! Reference source not found.	[128, 190] Error! Reference source not found.	[90, 190] Error! Reference source not found.
Week 28 c (Extended period of Part B)	197	[191, 204]					
Week 30 c (Extended period of Part B)	211	[205, 218]					
Week 32 c (Extended period of Part B)	225	[219, 232]					
Week 34 c (Extended period of Part B)	239	[233, 246]					
Week 36 c (Extended period of Part B)	253	≥247					

a **Error! Reference source not found.** Study days are calculated from the day of 1st injection of Part B. Study day = (date of assessment – 1st injection date +1) when date of assessment ≥ 1st injection date; otherwise study day = (date of assessment – 1st injection date). If patient never received any dose of study drug, randomization date will be used in place of 1st injection date.

b **Error! Reference source not found.** If unscheduled or ET visit occurs in this window and it is after the first dose of Part C, it will be considered for Week 26.

c Those are dummy analysis visits windows for patients with extended dosing in Part B. ET or unscheduled visit occurred after week 24 visit and before first dose of part C will be mapped per Table 5.

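### SAP Table 2 gives laboratory, PK and ADA data a Week 20 window in Part B although no such sample is scheduled then, so some early-termination samples form a spurious Week 20 row

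*Protocol*

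**What the plan says.** **Schedule.** In Protocol Section 8.1, Table 1, the row "Hematology, Chemistry" is marked at screening, baseline, week 12 and week 24. The week 20 cell (visit 10, day 141) is empty. Urinalysis has the same pattern. PK and ADA are marked at baseline, week 12 and week 24. SAP Table 6 repeats this. For laboratory tests only, SAP 4.5.2 lists after screening "baseline visit (visit 3), week 12, week 24, week 36, week 52 (EOS) or ET visits"; it does not cover PK or ADA.

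**Rule for building windows.** SAP 6.4: "The analysis visit windows will be created per study schedule of events (SOE) table for each parameter". The windows are used when data from the scheduled visit are unavailable, and to place early-termination (ET) and unscheduled visits.

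**Windows as printed.** In SAP Table 2 the column "Laboratory, PK, ADA" has [2, 113] for Week 12, [114, 155] for Week 20 and [156, 190] for Week 24.

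**Mapping rules in SAP 6.4.** Rule 1 reads: "If ET visit falls in an analysis window which has no missing value of this parameter, ET will be mapped to the next scheduled visit". Rule 4 reads: "If mapping distance is greater than 4 weeks, the unscheduled visit will not be mapped".

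**Use.** SAP 5.7.2 plans "Descriptive statistics of laboratory result and change from baseline by visit", and SAP 5.8 plans PK summaries at each sampling time. SAP 6.4 names laboratory and ADA data among those summarised by visit. Protocol 10.5 adds "No imputations for missing laboratory data, ECG data, vital sign data, or physical examination data will be made".

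**The concern.** The Week 20 window contradicts the SAP's own construction rule. Scheduled samples cannot fill it, so any Week 20 row for these parameters would consist only of ET and unscheduled samples. It would sit beside Week 12 and Week 24 rows that come mainly from patients seen on schedule, and a reader could take it for a planned assessment.

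The other side of the problem is the Week 24 row. Protocol Table 3 collects hematology, chemistry, urinalysis, PK and ADA at an ET visit. Rule 1 moves an ET sample forward only when its window already holds a value. Nothing is scheduled at week 20, so an ET sample from days 114 to 155 normally stays there. Laboratory values are not imputed, so nothing replaces it at Week 24.

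**Working it through.** **1. Reproduce the printed windows.** Each upper bound is the midpoint of consecutive target days, rounded down. The final bound, 190, is as printed.

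- Targets 85, 141 and 169: (85 + 141)/2 = 113 and (141 + 169)/2 = 155. The windows are [2, 113], [114, 155] and [156, 190], exactly as printed. The column was therefore built as if day 141 were a sampling day.
- The same three windows appear for PGIC and PGIS in SAP Table 1, where week 20 is scheduled.

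**2. Windows from the actual schedule.** Targets 85 and 169: (85 + 169)/2 = 127. The windows are [2, 127] and [128, 190].

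**3. Comparison within the SAP.**

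| Parameter | Scheduled | Windows in the SAP |
|---|---|---|
| EoE-IQ and similar PROs (Table 1) | weeks 12, 24 | [2, 127], [128, 190] |
| Eotaxin-3, IgE, IgG4 (Table 2) | weeks 4, 12, 24 | [2, 57], [58, 127], [128, 190] |
| Laboratory, Part C (Table 4) | weeks 36, 52 | [2, 141], [142, 218] |
| PK and ADA, Part C (Table 4) | weeks 32, 52 | [2, 127], [128, 218] |
| Laboratory, PK and ADA, Part B (Table 2) | weeks 12, 24 | [2, 113], **[114, 155]**, [156, 190] |

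Of these, only the last row has a window at a visit without a scheduled sample. The urine pregnancy test at week 20 does not explain it. That test is also done at weeks 4, 8 and 16, which have no laboratory window, and SAP 5.7.2 defines laboratory measurements as chemistry, hematology and urinalysis.

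**4. Where an ET sample goes.**

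| ET day | As written | Schedule-based, Week 12 value present | Schedule-based, Week 12 value absent |
|---|---|---|---|
| 114–127 (14 days) | Week 20 | Week 24, by rule 1 | Week 12 |
| 128–155 (28 days) | Week 20 | Week 24, directly | Week 24, directly |

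There is also an ambiguity just before this range. With a Week 12 value present, an ET sample from days 86 to 113 goes to the next scheduled visit. That is week 24 by the schedule but Week 20 by Table 2.

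**5. Where an unscheduled sample goes.** Rule 1 does not cover these, and rule 4 limits the distance to 28 days. As written, every day from 114 to 155 is within 28 days of day 141 (141 − 114 = 27; 155 − 141 = 14), so all can map to Week 20. Under schedule-based windows:

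- Days 141–155 are 28 to 14 days before day 169 and can map to Week 24.
- Days 128–140 are 41 to 29 days before day 169 and are not mapped.
- Days 114–127 are 29 to 42 days after day 85 and are not mapped.

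**6. Size.** Inputs are 70 patients per arm and 15% dropout (SAP 2.3), giving 0.15 × 70 = 10.5 dropouts per arm. Assumptions: dropouts are spread evenly over days 2 to 168 (167 days), and each attends an ET visit and gives samples.

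- Days 114–155: 42/167 × 10.5 = 2.6 per arm.
- Days 128–155, which need no Week 12 value: 28/167 × 10.5 = 1.8 per arm.
- Days 141–155, if the 4-week limit were also applied to ET visits: 15/167 × 10.5 = 0.9 per arm.

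**The case against.** The strongest reply is that little depends on this column. That is right. No efficacy endpoint or hypothesis test uses it. A reader might infer that safety information on early leavers is lost, but the documents do not support that:

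- SAP 5.7 looks for abnormalities from first injection to end of study, whatever the visit label.
- SAP 4.7 classifies ADA response per patient over all samples. Its persistent category needs positive samples more than 12 weeks apart in nominal time. A week 12 and ET pair would be 8 weeks apart if labelled Week 20 and 12 if labelled Week 24, so neither label qualifies.
- Individual PK plots use actual sampling time (SAP 5.8).
- Protocol 10.5 keeps extra laboratory assessments in listings and summaries.

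A reader might also infer that every sample from days 114 to 155 belongs in Week 24. Steps 4 and 5 show otherwise: days 114 to 127 depend on the Week 12 value, and unscheduled samples reach Week 24 only from days 141 to 155.

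The size is an upper bound. Patients who stop study drug are asked to keep attending scheduled visits (Protocol 7.4.2), so many will have a true week 24 sample. Only those leaving the study are asked to attend an ET visit (Protocol 8.1.2), and some may not come.

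Finally, Week 20 is closer than Week 24 to the true time of a day-141 sample. That is fair as a preference, but the SAP has chosen schedule-based windows and accepts the same displacement for EoE-IQ and eotaxin-3. The inconsistency stands.

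**Conclusion.** The Week 20 window for laboratory, PK and ADA data is an error against the SAP's own rule and schedule, and it is minor. As written, ET samples from days 114 to 155 create a Week 20 row that no scheduled sample supports. At most about 1.8 to 2.6 patients per arm are affected, given 15% dropout, even timing and full ET attendance. The upper figure also requires a Week 12 value for those leaving on days 114 to 127. If the 4-week limit is read as covering ET visits, the figure is about 0.9.

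The effect is confined to by-visit descriptive summaries of laboratory, PK and ADA data. Efficacy results, counts of potentially clinically significant values and patient-level ADA status are unaffected.

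**What to change.** In the laboratory, PK and ADA column of SAP Table 2, delete the Week 20 window, set Week 12 to [2, 127] and set Week 24 to [128, 190]. This changes three cells and needs no new data or procedures. The split is the one SAP Table 1 uses for EoE-IQ and SAP Table 2 uses at the week 12/24 boundary for eotaxin-3 and IgE. If a Week 20 window was intended, the SAP should say why and reconcile it with Sections 4.5.2 and 6.4 and Table 6.

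It would help to state at the same time whether the 4-week limit in rule 4 applies to ET visits, since the number of samples moved depends on it.

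There is a small cost. Some ET samples taken up to 169 − 128 = 41 days before day 169, or 169 − 114 = 55 days via rule 1 within the range considered here, would be labelled Week 24. Unscheduled samples from days 114 to 140 would no longer be mapped to any visit.

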8.1.1. Footnotes for the Schedule of Events Tables

8.1.1.1. Footnotes for Table 1

1. For patients without a satisfactory prior endoscopy/biopsy (eg, histological criteria were not met, or the biopsy was not performed while patient was on at least 8 weeks of high-dose PPI treatment), the screening period will be extended for up to 12 weeks (day -85) to allow for at least 8 weeks of high-dose PPI treatment prior to the screening endoscopy/biopsies. For all other patients, the screening period will be shorter, with sufficient time to allow screening assessments and laboratory test results to be available prior to the baseline endoscopy/biopsies.
2. The endoscopy/EoE-EREFS/biopsy procedures should be performed after all other efficacy and safety assessments.
 - a. The baseline endoscopy with biopsies should be performed at approximately day -21 ± 7 days to allow for availability of the intraepithelial eosinophil count result from the central pathology laboratory prior to day 1. For patients without a satisfactory prior historical endoscopy/biopsy, the baseline endoscopy/biopsies must be performed after at least 8 weeks of high-dose PPI. Patients may be randomized as soon as their endoscopy/biopsy results are available and DSQ eDiary entries are completed.

Note: Biopsy specimens from the stomach and/or duodenum will be obtained in all patients <18 years of age to rule out alternate etiologies. Stomach and/or duodenal biopsies will be obtained in adults only in the event of abnormal endoscopic findings (other than typical EoE findings) or clinical suspicion of alternate etiologies.

- b. For patients who receive rescue treatment during the double-blind treatment period, the endoscopy/EoE-EREFS/biopsy procedures will be performed prior to the initiation of rescue treatment. Patients undergoing endoscopy/biopsy prior to rescue will not undergo the scheduled endoscopy/biopsy at week 24

Note: All randomized patients found to have stomach and/or duodenal abnormalities at baseline will have follow-up stomach and/or duodenal biopsies at week 24 and week 52.

- c. The EndoFLIP procedure to measure esophageal distensibility may be performed during the esophagogastrosocopy procedures at selected North American sites in approximately 150 adult patients.
3. Assessments indicated for this week 24 (end of treatment) visit should be performed for all patients in Parts A and B. For patients who will enter Part C, there are additional events listed in week 24 visit in [Table 2](#) for Part C.
4. Patients may be re-screened once if they fail the screening evaluation, unless the reason for screen failure is related to histologic or clinical disease severity inclusion criteria. The baseline endoscopy with biopsy and EoE-EREFS scoring will not be repeated for re-screened patients. These results will continue to be valid baseline data. Re-screening must occur within 6 months of the screen failure.

5. Patients and/or caregivers will be trained on administration of study drug at a minimum at visit 3/day 1
6. On scheduled in-clinic study visit days, study drug will be administered in the clinic (by the patient, site staff, or caregiver). Study drug will be provided for those doses scheduled to be administered at home before the next in-clinic visit. Doses of study drug administered at home should be administered 1 week after the prior dose of study drug. Study drug administration that occurs in clinic should occur per the Schedule of Events in [Table 1](#) and [Table 2](#). Patients will be closely monitored at the study site at visits 3 to 6 for a minimum of 30 minutes after the administration of study drug. In addition to the predose assessments, AEs and vital signs (body temperature, blood pressure, respiratory rate and heart rate) will be assessed at 30 minutes (± 10 minutes) post-dose.
 - a. If COVID-19 restrictions limit the availability of staff or the patient to have in-clinic visits, after visit 3/day 1 patients/caregivers may be dispensed study drug for at-home dosing. Additionally, if the visit 11/week 24 endoscopy with biopsies is delayed due to COVID-19 restrictions, extended blinded dosing of study drug is allowed until this visit can occur. If extended dosing of the study drug occurs beyond week 23, the clinic staff must contact the patient every 4 weeks (at a minimum) to collect any AE (including ISRs), any change in concomitant medications and/or procedures, and monthly pregnancy test results, if required.
7. Assessments will be performed and blood samples will be collected before the administration of study drug.
 - a. If COVID-19 restrictions limit the availability of staff or the patient to have in-clinic visits, procedures/sample collection should occur at the next available in-clinic visit. Pregnancy testing must be performed as indicated (in-clinic or at-home) monthly (at a minimum) and results reported in a timely manner.
8. DSQ eDiary will be completed once daily by the patients after their last meal of the day but before they go to bed. Site personnel should conduct regular checks of patient eDiary compliance.
9. Patient Global Impression of Change (PGIC) of Dysphagia and Patient Global Impression of Severity (PGIS) of Dysphagia will be completed by the patient via electronic questionnaire at the indicated site visits. See [Section 8.2.2.5](#) and [Section 8.2.2.6](#).
10. EoE Impact Questionnaire and EoE Symptom Questionnaire will be completed by the patient via electronic questionnaire at the indicated site visits. See [Section 8.2.2.3](#) and [Section 8.2.2.4](#).
11. Total Nasal Symptom Score (TNSS) and Rhinoconjunctivitis Quality of Life Questionnaire for patients aged 12+ years [RQLQ(S)+12] will be administered only to patients with a documented history of allergic rhinitis; Asthma Control Questionnaire-5 (ACQ-5) will be administered only to patients with a documented history of asthma; Patient-Oriented Eczema Measure (POEM) will be administered only to patients with a documented history of AD. TNSS, POEM, ACQ-5 and RQLQ(S)+12 will be completed via electronic questionnaire and at the indicated site visits. The questionnaires will be administered only to the subset of patients who fluently speak the language in which the questionnaire is

presented (based on the availability of validated translations in participating countries). See Section 8.2.2.7, Section 8.2.2.8, Section 8.2.2.9, and Section 8.2.2.10.

12. EoE-EREFS should be completed by the investigator before biopsies for all patients are performed. For Part B enrolled patients, EoE-EREFS will be performed by both the investigators who perform the endoscopies as well as a centralized reading center, that will provide EoE-EREFS analysis and scoring from endoscopy imaging. For all endoscopies, the investigators will assess minor esophageal features including mucosal inflammatory and remodeling features.
13. At visits 3 through 6, vital signs (body temperature, blood pressure, respiratory rate, heart rate) should be taken predose and 30 minutes (± 10 minutes) post-dose. Vital signs should be taken predose at all other indicated visits.
 - a. If study drug administration is not possible in-clinic due to staff or patient availability due to COVID-19 restrictions, vital signs pre- and post-dose may not be performed.
14. For adolescent patients only.
15. Includes HIV Ab, HBsAg, HBsAb, HBcAb, HCV Ab, and TB. Tuberculosis testing will be performed on a country-by-country basis according to local guidelines if required by regulatory authorities or ECs.
16. Not required if post-menopausal status confirmed at screening. A negative result must be obtained prior to the randomization visit. In case of a positive urine test, the study treatment will be withheld and a serum pregnancy test to confirm the pregnancy should be performed as soon as possible. A confirmed pregnancy will lead to study drug discontinuation in all cases.
17. The EQ-5D-3L should be administered one time at either visit 1 or visit 3 for newly screened patients.
18. If COVID-19 restrictions limit the availability of staff or the patient to have in-clinic visits, the clinic staff should make every effort to contact the patient at the timepoint of the expected in-clinic visit to collect any AEs (including ISRs), any change in concomitant medications and/or procedures, and monthly pregnancy test results, if required.

8.1.1.2. Footnotes for Table 2

1. This visit is the same as the week 24 visit for Parts A and B (Table 1), and all other assessments indicated for week 24 of Parts A and B (Table 1) should be performed. All pre-dosing procedures (including endoscopy with biopsy) at visit 11/week 24 must be completed prior to administration of study drug for Part C extended active treatment.
2. Study assessments will be performed and blood samples will be collected prior to administration of study drug.
 - a. If COVID-19 restrictions limit the availability of staff or the patient to have in-clinic visits, procedures/sample collection should occur at the next available in-clinic visit. Pregnancy testing must be performed as indicated (in-clinic or at-home) monthly (at a minimum) and results reported in a timely manner.

3. Patients will be closely monitored at the study site at visits 11 (at a minimum) and 12, if possible, for a minimum of 30 minutes after the administration of study drug. In addition to predose assessments, AEs and vital signs (body temperature, blood pressure, respiratory rate, and heart rate) will be assessed at 30 minutes (± 10 minutes) post-dose.
4. All pre-dosing procedures (including endoscopy with biopsy) at the scheduled visit 11/week 24 must occur prior to dosing with Part C / extended active treatment study drug. On scheduled in-clinic study visit days, study drug will be administered in the clinic (by the patient, site staff, or caregiver). Study drug will be provided for those scheduled doses to be administered at home before the next in-clinic visit. Doses of study drug administered at home should be administered 1 week after the prior dose of study drug. Study drug administration that occurs in clinic should occur per the Schedule of Events in [Table 1](#) and [Table 2](#).
 - a. If COVID-19 restrictions limit the availability of staff or the patient to have in-clinic visits, after visit 11/week 24 patients/caregivers may be dispensed study drug for at-home dosing. Additionally, if the visit 19/ week 52 endoscopy with biopsies is delayed due to COVID-19 restrictions, extended dosing of study drug is allowed until this visit can occur. If extended dosing of the study drug occurs beyond week 51, the clinic staff must contact the patient every 4 weeks (at a minimum) to collect any AEs (including ISRs any change in concomitant medications and/or procedures, and monthly pregnancy test results, if required).
5. DSQ eDiary will be completed once daily by the patients after their last meal of the day but before they go to bed. Site personnel should conduct regular checks of patient eDiary compliance.
6. PGIC and PGIS will be completed by the patient via electronic questionnaire at the indicated site visits. See [Section 8.2.2.5](#) and [Section 8.2.2.6](#).
7. EoE Impact Questionnaire and EoE Symptom Questionnaire will be completed by the patient via electronic questionnaire at the indicated site visits. See [Section 8.2.2.3](#) and [Section 8.2.2.4](#).
8. TNSS and RQLQ(S)+12 will be administered only to patients with a documented history of allergic rhinitis; ACQ-5 will be administered only to patients with a documented history of asthma, and POEM will be administered only to patients with a documented history of AD. TNSS, POEM, ACQ-5 and RQLQ(S)+12 will be completed via electronic questionnaire and at the indicated site visits. The questionnaires will be administered only to the subset of patients who fluently speak the language in which the questionnaire is presented (based on the availability of validated translations in participating countries). See [Section 8.2.2.7](#), [Section 8.2.2.8](#), [Section 8.2.2.9](#), and [Section 8.2.2.10](#).
9. EoE-EREFS should be completed by the investigator before biopsies for all patients are performed. For Part B enrolled patients, EoE-EREFS will be performed by both the investigators who perform the endoscopies as well as a centralized reading center who will provide EoE-EREFS analysis and scoring from endoscopy imaging. For all endoscopies, the investigators will assess minor esophageal features including mucosal inflammatory and remodeling features.

10. Endoscopy/EoE-EREFS/biopsy procedures should be performed after all other efficacy and safety assessments. The EndoFLIP procedure to measure esophageal distensibility may be performed during the esophagogastroscope procedures at selected North American sites in approximately 150 adult patients.

Note: All randomized patients found to have stomach and/or duodenal abnormalities at baseline will have follow-up stomach and/or duodenal biopsies at weeks 24 and 52.

a. For patients who receive rescue treatment, endoscopy/EoE-EREFS/biopsy procedures will be performed prior to initiation of rescue treatment. Patients undergoing endoscopy/biopsy prior to rescue will not undergo the scheduled endoscopy/biopsy at weeks 24 and 52.

11. At visits 11 and 12, vital signs (body temperature, blood pressure, respiratory rate, heart rate) should be taken predose and 30 minutes (± 10 minutes) post-dose. Only predose vital signs are required at subsequent visits.

12. For adolescents only

13. In case of a positive urine pregnancy test, the study treatment will be withheld and a serum pregnancy test to confirm the pregnancy should be performed as soon as possible. A confirmed pregnancy will lead to study drug discontinuation in all cases.

14. If COVID-19 restrictions limit the availability of staff or the patient to have in-clinic visits, the clinic staff should make every effort to contact the patient at the timepoint of the expected in-clinic visit to collect any AEs (including ISRs), any change in concomitant medications and/or procedures, and monthly pregnancy test results, if required.

8.1.1.3. Footnotes for Table 3

1. Patients who are withdrawn from study drug will be asked to complete the 12-week follow-up period and the end of study visit.
2. DSQ eDiary will be completed once daily by the patients after their last meal of the day but before they go to bed. Site personnel should conduct regular checks of patient eDiary compliance.
3. PGIC and PGIS will be completed by the patient via electronic questionnaire at the indicated site visits. See Section 8.2.2.5 and Section 8.2.2.6.
4. EoE Impact Questionnaire and EoE Symptom Questionnaire will be completed by the patient via electronic questionnaire at the indicated site visits. See Section 8.2.2.3 and Section 8.2.2.4.
5. TNSS and RQLQ(S)+12 will be administered only to patients with a documented history of allergic rhinitis; ACQ-5 will be administered only to patients with a documented history of asthma, and only in countries in which a valid translation is available; POEM will be administered only to patients with a documented history of AD. TNSS, POEM, ACQ-5 and RQLQ(S)+12 will be completed via electronic questionnaire and at the indicated site visits. See Section 8.2.2.7, Section 8.2.2.8, Section 8.2.2.9, and Section 8.2.2.10.

6. EoE-EREFS should be completed by the investigator before biopsies for all patients are performed. For Part B enrolled patients, EoE-EREFS will be performed by both the investigators who perform the endoscopies as well as a centralized reading center who will provide EoE-EREFS analysis and scoring from endoscopy imaging. For all endoscopies, the investigators will assess minor esophageal features including mucosal inflammatory and remodeling features.
7. Endoscopy/EoE-EREFS/biopsy procedures should be performed after all other efficacy and safety assessments. The EndoFLIP procedure to measure esophageal distensibility may be performed during the esophagogastroscope procedures at selected North American sites in approximately 150 adult patients.

Note: All randomized patients found to have stomach and/or duodenal abnormalities at baseline will have follow-up stomach and/or duodenal biopsies at weeks 24 and 52 or ET visit.

- a. For patients who receive rescue treatment during the double-blind treatment period, endoscopy/EoE-EREFS/biopsy procedures will be performed prior to initiation of rescue treatment. Rescue treatment should not be delayed if an endoscopy with biopsies cannot occur due to COVID-19 restrictions. Patients undergoing endoscopy/biopsy prior to rescue will not undergo the scheduled endoscopy/biopsy at weeks 24 and 52.
8. Endoscopy/EoE-EREFS/biopsy will be performed only if the Unscheduled Visit is for the purpose of administering rescue therapy.
9. For adolescents only.
10. If COVID-19 restrictions limit the availability of staff or the patient to have in-clinic visits, the clinic staff should make every effort to contact the patient at the timepoint of the expected in-clinic visit to collect any AEs (including ISRs), any change in concomitant medications and/or procedures, and monthly pregnancy test results, if required.

